12.5 Role of the Research / Medical Monitor (RM)

The RM for this protocol will participate as a subject matter expert on the DSMB and will also conduct an independent review of study personnel's responses to study participants who experience suicidal crisis or one of the safety outcomes in the context of study-related activities. If study personnel (such as research

coordinators, or clinic/ED staff or providers) become aware of urgent clinical needs of a participant (such as imminent risk of self-harm) during study enrollment or one of the outcome assessments, that individual's needs should be placed above any responsibilities related to the study protocol. The goal of the RM review is to monitor this when potential issues are flagged by the PI and help ensure that study personnel are prioritizing individual participant's urgent clinical needs appropriately.

13. Data Collection & Management

13.1 Data Collection

Baseline data are either already collected and recorded in EPIC as standard of care for all patients (demographic data, C-SSRS) or will be completed by the participant via REDCap survey immediately following enrollment and informed consent (Baseline Survey). Outcome data will be collected via REDCap survey or over the phone at 6 months and 12 months. *Table 4* includes a list of all study variables for the primary analysis, the tool to be used for data collection or source of the data, the frequency/timing with which they will be collected, whether they are routinely collected or will be collected specifically for the SPARC Trial, and which entity will collect them. Patient and provider satisfaction surveys will collect additional quantitative and qualitative data and will be collected via REDCap survey.

Table 4: SPARC Trial Variables of Interest and Other Data Elements

Variable	Tool/Source	Routinely collected as standard of care	Mode of contact	Who will collect
Outcomes (6 months)				
Suicidal ideation & behavior	C-SSRS	No	REDCap survey (text, email, or phone)	SLHS
Recent suicide attempts, suicide completion, & self-harm; lethal means	6- and 12-Months Suicide Attempts Survey, Vital Records, EPIC	No	REDCap survey (text, email, or phone)	SLHS
Loneliness	NIH Toolkit Loneliness Scale	No	REDCap survey (text, email, or phone)	SLHS
Uptake of outpatient mental health treatment	Self-report, EPIC, Claims data	Yes	REDCap survey (text, email, or phone)	SLHS

Return to ED for suicidality	Self-report, EPIC, EDIE, Claims data	Yes	REDCap survey (text, email, or phone)	SLHS
Outcomes (12 Months)				
Suicidal ideation & behavior	C-SSRS	No	REDCap survey (text, email, or phone)	SLHS
Recent suicide attempts, completion, & self-harm; lethal means	6- and 12-Months Suicide Attempts Survey; Vital Records, EPIC	No	REDCap survey (text, email, or phone)	SLHS
Loneliness	NIH Toolkit Loneliness Scale	No	REDCap survey (text, email, or phone)	SLHS
Uptake of outpatient mental health treatment	Self-report, EPIC, Claims data	Yes	REDCap survey (text, email, or phone)	SLHS
Return to ED for suicidality	Self-report, EPIC, Claims data, EDIE	Yes	REDCap survey (text, email, or phone)	SLHS

Exposures (Baseline)				
Age in years, age category (adult/peds)	EPIC	Yes	n/a	SLHS
Sex	EPIC	Yes	n/a	SLHS
Race and ethnicity	EPIC	Yes	n/a	SLHS
Address including Zip code of residence (urban/rural)	EPIC	Yes	n/a	SLHS
County of residence (urban/rural)	EPIC	Yes	n/a	SLHS
Gender identity & sexuality	Baseline Survey	No	REDCap survey (In-person, phone, or video chat)	SLHS
Marijuana and drug use	Baseline Survey	No	REDCap survey (In-person, phone, or video chat)	SLHS
Alcohol use	Baseline Survey	No	REDCap survey (In-person, phone, or video chat)	SLHS
Religion	Baseline Survey	No	REDCap survey (In-person, phone, or video chat)	SLHS
Socioeconomic status (employment, education / maternal education, housing stability, income)	Baseline Survey	No	REDCap survey (In-person, phone, or video chat)	SLHS
History of suicide attempts & self-harm; lethal means	Baseline Suicide Attempts Survey	No	REDCap survey (In-person, phone, or video chat)	SLHS
Insurance Provider	EPIC	Yes	n/a	SLHS
Suicidal ideation & behavior at baseline (standard of care)	C-SSRS (in EPIC)	Yes	n/a	SLHS
Suicidal ideation & behavior at baseline (ED only, self-report)	C-SSRS / Baseline Survey (ED only)	No	REDCap survey (In-person, phone, or video chat)	SLHS
Quality of life at baseline	Euro-Qol	No	REDCap survey (In-person, phone, or video chat)	SLHS
Loneliness	NIH Toolkit Loneliness Scale	No	REDCap survey (text, email, or phone)	SLHS
Antidepressant and Lithium use	EPIC	Yes	n/a	SLHS
Clinic or ED name	EPIC	Yes	n/a	SLHS

Intervention assignment	REDCap	No	n/a	SLHS
Patient Satisfaction Survey (2 weeks & 12 months)				
Patient satisfaction with interventions	Patient Satisfaction Survey	No	REDCap survey (text, email, or phone)	SLHS
Provider Satisfaction Survey (Year 1 or 2)				
Provider satisfaction with interventions and suicide prevention workflows	Provider Satisfaction Survey	No	REDCap survey (email, Provider Portal, or other)	SLHS
Process Variables				
Screening rates by clinic and provider	EPIC	Yes	n/a	SLHS
Rate of safety planning by clinic	EPIC	Yes	n/a	SLHS
“Dose” of follow-up contact: timing, type (phone vs text), and number of attempted and successful contacts from the Hotline	Hotline	No	n/a	Hotline
“Dose” of Caring Contact text messages: date/time of each text message sent (* 25 text messages)	Hotline	No	n/a	Hotline
Other Variables				
Medical record number	EPIC	Yes	n/a	SLHS
Encounter date(s) and time(s)	EPIC	Yes	n/a	SLHS
Clinic specialty/type	EPIC	Yes	n/a	SLHS
Provider(s)	EPIC, Claims data	Yes	n/a	SLHS
Referral(s) related to behavioral health	EPIC	Yes	n/a	SLHS
Does cell or landline phone on record belong exclusively to study participant or is it shared?	Baseline Survey	No	REDCap survey (in person, phone, or video chat)	SLHS
Alternative modes of contact	Contact Form	No	REDCap survey (in person, phone, or video chat)	SLHS
Death	State Vital Records	Yes	n/a	Idaho Department of Health & Welfare

13.2 Data Management

This study will employ a comprehensive data management plan. Study data will be directly entered in REDCap or Mosio (a HIPAA-compliant text messaging platform) or will be exported from Epic and uploaded to REDCap by study staff. Down-time procedures utilizing paper-based surveys and forms to collect data from participants will be developed. Paper forms and surveys that include PHI will be kept secure according to standard procedures by clinical staff and study staff. Each patient will be assigned a unique identifier and allocated to one of the two intervention arms based on random assignment using appropriate software. The statistics team will compile study data from REDCap on a routine basis for reports and to build and maintain a

complete dataset. To protect the confidentiality of participants, data and associated documentation will be available to the PI and trained study staff only, under a data-sharing agreement that includes a commitment to: (1) use the data only for research purposes or to ensure participant safety, (2) secure the data using appropriate computer technology, (3) destroy or return the data after analyses are completed, and (4) not further distribute the data outside specified members of the research team in compliance with SLHS Research data privacy and sharing practices and policy. The University of Washington Institute of Translational Health Sciences (ITHS) hosts REDCap, a secure, HIPAA-compliant web application, which will be used for building and managing online surveys and databases for this research. ITHS provides REDCap support and an array of research data curation and storage support. Other databases (such as Access, Excel) may be used for study management purposes; all such data will be kept on secured, password-protected computers.

Provider satisfaction surveys will be captured in REDCap as confidential surveys and provider and staff email addresses will be stored in REDCap and/or on secured password-protected computers.

14. Statistical Analysis

14.1 General Analytic Approach

The primary analysis will compare the effectiveness of the two interventions delivered in the two settings (EDs and primary care), accounting for the other covariates of interest. Potential confounding, effect modification, and mediation will be handled through study design (e.g. individual randomization), through stratification (age category), and use of multilevel modeling to account for geographic clustering. Other published studies related to caring contacts and safety planning with and without follow-up have shown that the selected patient-centered outcomes change over a 6-12-month period in response to receipt of these interventions.^{24,63}

All data analyses will be completed using appropriate statistical software (such as R and R Studio, SPSS, Stata, SAS, Python, and/or Microsoft Excel).

Statistical significance will be determined based on a type I error (alpha) of 0.05 (two-sided). Confidence intervals will be reported in addition to p-values.

Aim 1: Analyses will be stratified for adults and adolescents, modeling the effects of intervention separately in these age groups. There is very little evidence regarding the effect of safety planning, caring contacts, or follow-up phone calls on adolescent populations, and we hypothesize that the magnitude of effect may differ by age group. Generating evidence of the effectiveness of these interventions in suicidal adolescents is the primary goal of this heterogeneity of treatment effect (HTE) analysis. **Appropriate statistical analyses will be used to determine whether outcomes differ between the intervention arms.**

Interaction between the interventions and settings will be assessed. Variables will be measured at baseline and reported using descriptive statistics. Potential effect modifiers will be assessed and include age, sex, gender identity, sexuality, race/ethnicity, religion, urban/rural residence, drug/alcohol use,

suicidal ideation and behavior at baseline, baseline quality of life, baseline loneliness, medication use, measures of socioeconomic status and/or other variables related to the specified outcomes of interest. Data will be analyzed according to both an intention to treat protocol and per protocol received. Please see section 5.4 Populations for Analyses for further detail.

This study will report the distribution of key variables to facilitate assessment of the study's internal and external validity. At a minimum, this study will report the distribution of key variables within the analytic population (key variables are defined as those that are included in the causal diagram at the beginning of the *Research Design* section of this Research Plan). Missing data will be assessed on a regular basis through routine data reports. These reports will allow the investigators to assess the cause of missing or anomalous entries, and address these if possible. If missing values cannot be retrieved, the reason for the missingness will be recorded in data comments available through REDCap. Study staff will record the reason for any participant drop-out during the 12 months of follow-up.

Aims 2 & 3: Descriptive statistics will be used to summarize quantitative survey results.

14.2 Power & Sample Size

Power and sample size calculations for the primary analysis are summarized for each of the age population strata below:

- **Adults**: in order to have 90% power to detect a difference of 1 unit in the primary outcome (C-SSRS score), SD=2, allowing for up to 30% dropout, the study requires a sample size of 790
- **Adolescents**: in order to have 80% power to detect a difference of 1 unit in the primary outcome (C-SSRS score), SD=2, allowing for up to 30% dropout, the study requires a sample size of 592

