5.1 Study Design

5.1.1 Aim 1: Randomized Controlled Trial

Aim 1 (primary analysis) is a randomized controlled trial with individual patients randomly assigned to receive either SPI+ or SP+CC. The study objectives and primary outcomes pertain to the individual level.

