5.2 Randomization

Randomization will occur at the individual level. Patients will be randomized to either SPI+ or SP+CC by the study statistician using appropriate software.

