9.2 Primary Outcome & Assessment

The primary outcome of interest (suicidal ideation and behavior) and the secondary outcomes (loneliness, uptake of outpatient mental healthcare services, and ED utilization for suicidality) were selected because these are the outcomes that people with lived experience with suicide (PLES) and the Provider Advisory Board (PAB) indicated were most important to patients, caregivers, and providers.

Outcomes will be measured at baseline (immediately prior to study enrollment as part of usual care for all patients (suicide risk) or immediately following study enrollment (loneliness)), and at 6 months (+/- 4 weeks), and 12 months following study enrollment (+/- 4 weeks).

Aim 1: The primary outcome is reduced suicidal ideation and behavior (measured as change from baseline score at 6 and 12 months using the Columbia Suicide Severity Rating Scale (C-SSRS)).^{1,15,16,47} The C-SSRS is widely used in practice and research, and has strong psychometric properties for use with both adult and adolescent populations, which are summarized in a *Supporting Evidence* document.¹⁶ The C-SSRS was developed in American English and has been translated to multiple languages; the Spanish language version has been validated.^{16,48} The C-SSRS has been shown to be an effective tool to measure suicidality (diagnosis) and is sensitive to change over time, which allows measurement of the effect of treatment at 6 and 12 months.^{16,49}

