14.4 Planned Interim Analyses

An interim analysis will be conducted at 50% enrollment (or as determined by the Data Safety and Monitoring Board) to assess grounds for early stopping if one of the arms is overwhelmingly more effective than the other.

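### Section 14.2: the printed inputs (1 unit, SD 2, 30% dropout) need about 246 adults and 183 adolescents, not 790 and 592, and nothing stated explains the 3.2-fold gap

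*Protocol*

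**What the plan says.** Section 14.2 gives one calculation per age stratum. For adults, the aim is 90% power for a difference of 1 unit in C-SSRS score: "SD=2, allowing for up to 30% dropout, the study requires a sample size of 790". For adolescents, the aim is 80% power for the same difference: "SD=2, allowing for up to 30% dropout, the study requires a sample size of 592". The synopsis adds 790 and 592 to a total of 1,382, so each figure covers both arms.

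The other inputs stand elsewhere in the protocol:

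- Section 14.1: "Statistical significance will be determined based on a type I error (alpha) of 0.05 (two-sided").
- Section 5.1.1: Aim 1 is a "randomized controlled trial with individual patients randomly assigned to receive either SPI+ or SP+CC". Section 5.2 repeats: "Randomization will occur at the individual level". No allocation ratio is given.
- Section 9.2: the primary outcome is "measured as change from baseline score at 6 and 12 months using the Columbia Suicide Severity Rating Scale".
- Section 14.1, on the analysis: "use of multilevel modeling to account for geographic clustering". No intraclass correlation, cluster size or design effect accompanies this.
- Section 14.4: "An interim analysis will be conducted at 50% enrollment", or when the DSMB decides. No adjustment of alpha or sample size is attached to it.

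**The concern.** A standardised difference of 1/2 = 0.5 is moderate, and 90% power for it takes fewer than 100 completers per arm. A requirement of 790 adults, or about 276 completers per arm after 30% loss, is far outside that range. The adolescent figure is too large by almost the same factor, so a slip in one number is an unlikely explanation.

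Section 14.2 is where the funder, the DSMB and later readers learn what difference the trial was built to find. Section 9.1.1 also relies on it when it says the study is powered for age-stratified results. If the printed difference, SD and power do not lead to the printed sample size, a null or small result cannot be read against the design: the reader does not know whether the target was 1 unit or about half that.

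**Working it through.** **Inputs.** Difference d = 1, SD = 2, power 90% (adults) and 80% (adolescents), dropout 30% (section 14.2); alpha 0.05 two-sided (14.1); two arms, individual randomisation (5.1.1, 5.2). Assumption: 1:1 allocation.

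**Attempt to reproduce the stated figures.** Completers per arm by normal approximation: n = 2 × (z₀.₉₇₅ + z_power)² × SD² / d².

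- Adults: 2 × (1.960 + 1.2816)² × 4 = 84.1, so 85 per arm; 170 / 0.7 = 243 enrolled.
- Adolescents: 2 × (1.960 + 0.8416)² × 4 = 62.8, so 63 per arm; 126 / 0.7 = 180 enrolled.

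The two-sample t-test (noncentral t) gives 86 and 64 per arm: 172 / 0.7 = 246 and 128 / 0.7 = 183. Neither method gives 790 or 592. The ratios are 790/246 = 3.21 and 592/183 = 3.23.

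**Is it a typing error?** The two stated figures stand in the ratio 790/592 = 1.334. The ratio expected from moving between 80% and 90% power is (3.2415/2.8016)² = 1.339. Both figures therefore seem to come from one formula with the same undisclosed factor.

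**Other readings the text might allow** (t-test and division by 0.7, except where marked):

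| Reading | Adults | Adolescents |
|---|---|---|
| Stated in 14.2 | 790 | 592 |
| Printed inputs | 246 | 183 |
| (a) SD 2 is for one time point; change score with baseline correlation 0 (assumed), SD = 2√2 = 2.83 | 486 | 363 |
| (b) Alpha split over two strata and two time points, 0.05/4 = 0.0125 | 332 | 260 |
| (c) Both (a) and (b) | 660 | 515 |
| (d) 3:1 allocation (normal approximation) | 320 | 239 |
| Difference of 0.5 unit instead of 1 (normal approximation) | 963 | 720 |

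None gives the stated pair. Readings (a) to (d) fall short and the last overshoots.

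**What the stated numbers deliver.** Completers per arm after 30% loss: 790 × 0.7 / 2 = 276.5 and 592 × 0.7 / 2 = 207.2.

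- Power for 1 unit at SD 2: 99.995% (adults) and 99.91% (adolescents).
- Difference detectable at the stated power, (z₀.₉₇₅ + z_power) × SD × √(2/n): 3.2415 × 2 × √(2/276.5) = 0.551 and 2.8016 × 2 × √(2/207.2) = 0.550. With SD 2.83 it is 0.78 in both strata.
- SD at which 1 unit fits the stated numbers: about 3.62 in both strata (t-test).

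**Clustering as the missing factor.** Setting 1 + (m − 1) × ICC equal to the ratio, with the site figures in section 6.1.1 as m, gives ICC = (3.215 − 1)/39 = 0.057 for 40 adults per site and (3.2375 − 1)/24 = 0.093 for 25 adolescents per site. The protocol states neither value.

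**The case against.** The strongest defence is that section 14.2 only summarises a calculation that included a variance inflation it does not print. Section 14.1 commits to a multilevel model, the excess is the same in both strata, and a SAP that is not at hand may give an intraclass correlation. With one common cluster size, say the average over all participants of 1,382/32 = 43.2 per site, a single ICC of about 0.053 would produce the factor in both strata. There are also signs of a clustered ancestor: section 9.1.1 still describes matching so that rural clinics are spread equally between groups, and reference 64 is a methods paper on cluster randomised trials that does not appear to be cited in the text.

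Part of this stands. An omitted common factor is plausible, and 790 and 592 need not be wrong as targets. The section 6.1.1 figures are site-eligibility thresholds rather than planned cluster sizes, so the ICCs derived from them are illustrative only. But the strata are modelled separately, and their own averages per site, 790/32 = 24.7 and 592/32 = 18.5, again need different ICCs. More to the point, section 14.2 says that the printed inputs require these numbers, and they do not. Clustering is named only for the analysis, and a design effect above 3 would itself need a justification when patients, not clinics, are randomised. A SAP could add the missing value, but it would not make the printed sentence true.

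It is also fair to say that no harm to power follows. On the printed inputs the trial is larger than it needs to be.

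**Conclusion.** The concern holds. On the printed difference, SD, power, dropout and alpha, with 1:1 allocation assumed, the requirement is 246 adults and 183 adolescents (243 and 180 by normal approximation), against 790 and 592 stated. Without a factor of about 3.2 that the protocol does not disclose, the stated sample size, power, difference and SD cannot all be right. Which element is wrong or missing cannot be settled from the protocol; a clustered calculation carried over from another design is only a possibility.

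The defect lies in the stated justification, not in the size of the trial, its estimates or its conduct. Its practical effect is on interpretation: if SD 2 applies to the change score, the trial is sized for about 0.55 unit, roughly half the difference it names. One side effect concerns the interim look. Half of enrolment is 395 adults and 296 adolescents, already above the full printed-input requirement, although not all of them would have outcome data by then. This should be fixed, but it is not a threat to the trial's validity.

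**What to change.** Keep the enrolment targets and restate section 14.2 so that difference, SD (and whether it refers to a single score or to change), power, alpha, allocation ratio, dropout and sample size agree.

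- If SD 2 for the change score and 1:1 allocation are correct, say that 790 and 592 with 30% loss give 90% and 80% power for about 0.55 unit, and more than 99.9% power for 1 unit.
- If another input was used, such as a larger SD, a smaller difference, a multiplicity or interim adjustment, or a design effect, print its value and justify it for individual randomisation and the multilevel model of section 14.1.

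Separately, reconcile the clinic-matching sentence in section 9.1.1 with the individual randomisation in sections 5.1.1 and 5.2.

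The cost is protocol wording. Enrolment and procedures do not change.

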14.3 Missing Data

Missing data will be addressed through statistical analysis. With proper inclusion of variables associated with the probability of missingness, we will assess the nature of missingness; if the missing data follow a 'missing at random' framework, we will use multiple imputation.⁶⁵ The most appropriate multiple imputation technique will be determined based on the distributions of missing data and observed variables.⁶⁶⁻⁶⁸ Multiple imputation methods incorporate the uncertainty of value estimation into parameter estimates. We will assess the sensitivity of estimates to the imputation approach and variables used in the imputation algorithm.

14.4 Planned Interim Analyses

An interim analysis will be conducted at 50% enrollment (or as determined by the Data Safety and Monitoring Board) to assess grounds for early stopping if one of the arms is overwhelmingly more effective than the other.

14.5 Sub-Group Analyses

We plan to generate different effect estimates for the following subgroups: low baseline C-SSRS score vs moderate to high baseline C-SSRS score, Hispanic vs non-Hispanic, female vs male, cisgender vs transgender or gender-nonconforming, heterosexual vs. homosexual or bisexual, and urban vs rural; however, this study has not been specifically powered to identify differing treatment effects in each of these subgroups.

15. Engaging Providers & People with Lived Experience with Suicide

The research team for this trial includes people with lived experience with suicide, research scientists, system-level medical directors and administrators, physicians and social workers in EDs and primary care at SLHS; community partners at Jannus, including the Hotline and Empower Idaho, and, the Idaho Federation of Families for Children’s Mental Health (IFF); suicide prevention researchers as well as dissemination, biostatistics, and bioethics experts at the University of Washington, the University of Pennsylvania, and Columbia University.

Study staff will continue to engage and expand the existing *People with Lived Experience with Suicide (PLES) Advisory Board to support this trial.* Study staff will convene a formal PLES Advisory Board to include up to 15 people who experienced suicidality as adults or adolescents either directly or through a loved one. The PLES Advisory Board will provide input related to specific questions (such as study branding, recruitment strategy, the informed consent process (including readability of consent forms), retention techniques, and the content and frequency of follow-up contact), and will assist with the design of the patient satisfaction surveys and dissemination strategy.

Study staff will continue to engage providers through SLHS for input on study design, conduct, and integration of this research into clinic workflows. Routine meetings will be held with providers and health system staff representing multiple perspectives, such as system- and clinic-level providers, patient access specialists, social workers, psychiatrists and psychologists, ED physicians, pediatricians, and primary care physicians, advanced practice providers, and medical assistants and nurses.

Study staff will continue to engage stakeholders at the state, regional, and community levels, such as public sector stakeholders, private foundations, and non-governmental organizations.

16. Risk / Benefit Analysis

